#### 7.1.4.3 Standard and procedures for stopping tests/trial treatment

The Sponsor has the right to discontinue a site or terminate the trial for the following reasons:

- The Sponsor may terminate the study for safety reasons
- A decision on the part of the Sponsor to suspend or discontinue testing, evaluation, or development of the product for any reason
- The Sponsor may decide to close a study site when the Investigator fails to enroll patients during the enrolment period
- Failure of the Investigator to comply with pertinent regulations of appropriate regulatory authorities
- Insufficient adherence to protocol requirements
- Submission of knowingly false information from the research facility to the Sponsor, the Sponsor's representatives or appropriate regulatory authorities

If the study is terminated early, all specified follow-up data on subjects enrolled prior to termination will be collected and reported

#### 7.1.4.4 Enrollment period and study duration

Up to 60 patients will be enrolled and implanted with the device at four sites in China over an estimated six month enrolment period with a follow-up period to 5 years. The study is expected to last 5.5 years

#### 7.1.5 Patient Screening and Data Collection

##### 7.1.5.1 Patient Screening and Enrolment

The study site shall have a committed Heart Team involved in the screening process. The Heart Team will include at least two cardiac surgeon, one interventional cardiologist, one radiologist, and one anesthesiologist but could also include (without being limited to) the following specialties:

- Echocardiography
- Gerontology

The screening of patients in cardiovascular and cardiac surgery departments will be conducted by one or more delegated study team members. The study team will be responsible for ensuring and reporting study patient screening for study eligibility. Cumulative screening and enrollment logs will be maintained by study sites. Reasons for screen failures will be documented in study logs.

To accommodate the implant procedure learning curve, a roll-in strategy will be available. Each study site will be allowed up to two roll-in patients. Edwards Lifesciences will document if the patient is a roll-in patient before the implant procedure begins. Roll-in patients will complete all study visits and procedures, and not be counted toward the 60 implanted patients.

In addition, the Heart Team will be required to assess all patients for study inclusion to ensure compliance to surgical risk criteria, screening procedures to assess valve size and delivery method, and other inclusion/exclusion criteria. After heart team identifies a patient, the Sponsor will review and confirm eligibility during the case review process.

All patients who sign a study informed consent will be entered into the database. Subjects will be included

in analysis of the trial if an Edwards' investigational device is inserted into the patient. Only patients that leave the procedure room with a SAPIEN 3 THV in place will be counted toward the 60 implanted patients.

#### 7.1.5.2 Data Collection

Study subjects will undergo screening and pre-procedure visits, and then follow-up visits at Discharge, and 30 Days (+14 days) for Endpoint analysis. Long-term follow-up data is collected at 6 Months (+/- 30 days), 1 Year (+/- 60 days), 2 Years (+/- 60 days), 3 Years (+/- 60 days), 4 Years (+/- 60 days), and 5 Years (+/- 60 days).

The Study Visit Schedule is outlined in Table 4 for enrolled subjects for the duration of the study from Screening and Baseline through the 30 Day visit (Primary Endpoint) and 5 year follow-up visits.

Table 2. Study Visit Schedule

	Screening	(≤30 days of procedure) Baseline	Procedure	Post-Procedure (Within 48 hours)	Discharge	30 Day Follow-Up (+14 days)	6 Month (+/-30 days)	1 Year (+/-60 days)	2-5 Years (+/-60 days)
Informed Consent	X								
Medical History	X								
Physical Exam	X				X	X		X	X
CSS Angina	X				X	X		X	X
NYHA Classification	X				X	X		X	X
STS Risk Score, Logistic EuroSCORE, and EuroSCORE II	X								
Operability Risk Assessment	X								
Cardiac Medications		X	X	X	X	X	X	X	X
Adverse Event Assessment			X	X	X	X	X	X	X
Frailty Assessment		X							
NIH Stroke Scale		X 		X 	X 	X 			
Modified Rankin Scale		X 		X 	X 	X 			
Six Minute Walk Test (6MWT)		X 				X 			
KCCQ Questionnaire		X				X			
Labs									

Hemoglobin, Hematocrit, Platelet Count and White Blood Cells		X		X	X	X			
PTT or PT/INR		X		X	X				
CK/CK-MB and/or Troponins		X 		X 		X			
Creatinine		X		X	X	X			
Liver Panel (ALT, AST)		X							
Albumin		X				X			
Non-Invasive Tests									
ECG		X		X	X	X		X	
Chest X-ray		X							
Transthoracic Echocardiogram (TTE)	X				X	X		X	X
Fluoroscopic imaging implanted valve			X			X 		X 	X 
Invasive Tests									
CT Thoracic/Abdomen with visualization of iliac and femoral arteries	X								
Cardiac Catheterization or CT angiogram	X								
Supra-aortic Angiogram or (TEE)	X		X						
Invasive hemodynamics			X						

 Collection of adverse events begins when the patient starts the procedure. This is defined as when anesthesia is first administered

Every effort should be made to have a neurologist or neurology fellow perform the neurological assessments. If the neurologist or neurology fellow is not available, a certified team member may perform the tests.

Patients are exempt from the 6 Minute Walk Test if they are contraindicated to complete the test. Contraindications must be documented in medical notes.

Baseline CK/CKMB and/or Troponins are required  $\leq$  72 hours before the procedure.

Post Procedure CK/CKMB and/or Troponins are required at 3 different time intervals: 1) the first lab draw post procedure (within 8 hours of exiting the cath lab or operating room) 2) the second lab draw 6 – 8 hours after the first lab draw 3) the third lab draw 6 – 8 hours after the second lab draw.

Transesophageal Echocardiogram (TEE) may be used if TTE is not available

For patients with abnormal findings related to valve integrity and position and patients with Adverse Events related to worsening valve function.

## Screening

The following screening data will be collected for all study patients to assess eligibility as per standard of care:

- Operability Risk Assessment
- Medical history, pertinent physical examination [include blood pressure, height, weight and all major systems findings]
- NYHA functional classification
- CSS Angina classification
- Risk assessment (STS Risk Score, Logistic EuroSCORE, and EuroSCORE II)
- Non-Invasive Studies (must be completed within 60 days before procedure date)
- Comprehensive transthoracic echocardiogram (TTE) (transesophageal echocardiogram (TEE) may be used as an alternative)

Invasive Studies (must be completed before the procedure date)

- Cardiac and abdominal CT angiogram of high quality with complete visualization to complete measurements of the aortic valve, aortic arch, both iliac and femoral arteries to the aorta. In the situation where patients have compromised renal function that precludes the use of contrast agents, MR imaging may be used as an alternative to CT ( $\leq 180$  days before procedure)
- Left heart catheterization to assess the severity of aortic stenosis and severity of coronary artery disease ( $\leq 180$  days before procedure)

If any assessments need to be completed or repeated outside of standard of care, a patient will need to sign a Patient Informed Consent prior to completing assessments.

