#### Disease Process

The pathophysiology of AS includes an increase in afterload, progressive hypertrophy of the left ventricle, and a decrease in systemic and coronary blood flow as consequences of valve obstruction. Typically, patients with AS are free from cardiovascular symptoms (e.g. angina, syncope and/or heart failure) until late in the course of the disease. However, once symptoms manifest, the prognosis is poor, especially when associated with congestive heart failure.

Death in general, including sudden death, occurs primarily in symptomatic patients. Survival analyses have demonstrated that the interval from onset of symptoms to time of death is approximately two years in patients with heart failure, three years in those with syncope, and five years in those with angina [2]. Among symptomatic patients with moderate-to-severe AS treated medically, mortality rates after the onset of symptoms were approximately 25% at 1 year and 50% at 2 years and more than 50% of deaths were sudden [3].

Grading the severity of AS is based on a variety of hemodynamic and natural history data. According to the ACC/AHA guideline authors, AS is best described as a continuum. In patients with moderate-to-severe AS, valve area may decline up to 0.3 cm^2 per year and the systolic pressure gradient across the valve can increase by as much as 15-19 mmHg per year, with a higher rate of progression observed in elderly patients with coronary artery disease

(CAD) and chronic renal insufficiency [4]. Relief of aortic valve obstruction typically results in an improvement of symptoms, hemodynamic parameters, and global left ventricle systolic function, as well as reversal of left ventricular hypertrophy [4,5].

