#### 7.1.4.1 Inclusion Criteria

Patients must meet all of the Inclusion Criteria in order to participate in the study

1. Subjects who are considered to be operable and high risk for surgical valve replacement: STS Score  $\geq 8$  and  $\leq 15$  or Logistic EuroSCORE  $\geq 15$  and  $\leq 40$ . If STS Score is below 8 and Logistic EuroSCORE is below 15, patients should have other clinical or anatomical risk factors that would be considered high risk for surgery and documented by the heart team
2. Severe symptomatic calcific aortic stenosis requiring aortic valve replacement characterized by one or more of the following within 60 days prior to the index procedure: AVA  $< 0.8 \text{ cm}^2$ , Indexed AVA  $< 0.5 \text{ cm}^2/\text{m}^2$ , mean gradient  $> 40\text{mmHg}$ , or peak aortic jet velocity  $> 4.0\text{m/sec}$ .
3. NYHA Functional Class II or greater.
4. The study patient or the study patient's legal representative has been informed of the nature of the study, agrees to its provisions and has provided written informed consent as approved by the EC of the respective clinical site.
5. The study patient agrees to comply with all required post-procedure follow-up visits.
6. Native aortic valve annulus area between  $273 \text{ mm}^2$  -  $683 \text{ mm}^2$  as measured by CT.
7. Native aortic annulus diameter between 18.6 mm – 29.5 mm as measured by CT.

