#### 7.1.4.2 Exclusion Criteria

Patients must not meet any of the Exclusion Criteria in order participate in the study

1. Evidence of an acute myocardial infarction  $\leq$  1 month (30 days) before the intended treatment [(defined as: Q wave MI, or non-Q wave MI with total CK elevation of CK-MB  $\geq$  twice normal in the presence of MB elevation and/or troponin level elevation (WHO definition)].
2. Aortic valve is a congenital unicuspid or is non-calcified.
3. Aortic valve is bicuspid and the patient is less than 60 years old, or the aortic valve is bicuspid with no raphe (Sievers classification type 0)
4. Anomalous coronary artery that would interfere with proper placement of the valve.
5. Mixed aortic valve disease (aortic stenosis and aortic regurgitation with predominant aortic regurgitation  $>3+$ ).
6. Pre-existing mechanical or bioprosthetic valve in any position.
7. Any therapeutic invasive cardiac procedure resulting in a permanent implant that is performed within 30 days of the index procedure. Implantation of a permanent pacemaker or ICD is not considered exclusion criteria.
8. Any patient with a balloon valvuloplasty (BAV) within 30 days of the procedure (unless BAV is a bridge to procedure after a qualifying echocardiogram).
9. Leukopenia (WBC  $<$  3000 cell/mL), acute anemia (Hgb  $<$  9 g/dL), Thrombocytopenia (Plt  $<$  50,000 cell/mL).
10. Renal insufficiency (creatinine  $>$  3.0 mg/dL) and/or renal replacement therapy at the time of screening.
11. Untreated clinically significant coronary artery disease requiring revascularization.
12. Emergency interventional/surgical procedures within one month (30 days) prior to the TAVI procedure.
13. Hypertrophic cardiomyopathy (HCM with myocardium more than 1.5cm without an identifiable cause) with or without obstruction (HOCM).
14. Severe ventricular dysfunction with LVEF  $<$  20%.
15. Echocardiographic evidence of intracardiac mass, thrombus or vegetation.
16. Active upper GI bleeding within 3 months (90 days) prior to procedure.
17. A known contraindication or hypersensitivity to all anticoagulation regimens, or inability to be anticoagulated for the study procedure.
18. Stroke or transient ischemic attack (TIA) within 3 months (90 days) of the procedure.
19. Estimated life expectancy  $<$  12 months (365 days) due to carcinomas, chronic liver disease, chronic renal disease or chronic end stage pulmonary disease.

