## Baseline

Assessments and laboratory tests are required to be completed within 30 days prior to the procedure date. Assessments and laboratory tests completed outside of the 30 days will need to be repeated. If completed outside of standard of care, then a Patient Informed Consent Form will need to be signed first.

The following Baseline data will be collected for all study patients prior to procedure:

- Current cardiac medications and all medications given for cardiovascular effect;
- Neurological assessment
  - National Institutes of Health Stroke Scale (NIHSS) (Appendix C)
  - Modified Rankin Scale (mRS) (Appendix D)
- Frailty Assessment (Appendix E)

- Six Minute Walk Test (Appendix F)
- Kansas City Cardiomyopathy Questionnaire (KCCQ) (Appendix G)
- Clinical Laboratory Tests
  - Blood count (hemoglobin, hematocrit, platelet count, white blood cells)
  - PTT or PT/INR
  - CK/CK-MB and/or Troponins
  - Creatinine
  - Liver Panel (ALT, AST)
  - Albumin
- Non-invasive studies
  - 12-Lead ECG
  - Chest x-ray

Procedure

Transfemoral access technique will be used by the investigator in his/her normal practice of interventional cardiology and patient selection process.

Recommended Antiplatelet/Anticoagulation Regimen

Table 4 outlines the recommended antiplatelet regimen. The categories were developed by The PARTNER II Trial Patient and Procedure Management Steering Committee. There are no current validated guidelines in this specific study population, however, the literature was surveyed and used as guidance for the following proposed guidelines. It is expected that specific agents and dosing regimens may vary from site to site. Patients will be assessed by the heart team for Category of Stroke Risk prior to prescribing treatment regimen. The Category and specific treatment regimen will be documented in the discharge case report form. Committee Categories are based on CHADS 2 score for stroke risk [27].

NOTE: The CHADS 2 score only applies to patients in atrial fibrillation (AF) and has not been validated in non-AF patient populations; therefore the CHADS 2 score reference was used as one among many guidelines to establish the risk stratification for intensity of anticoagulation regimen.

Table 3. Summary of Recommended Antiplatelet/Anticoagulation Therapy

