### 8.4 Statistical method for all data, together with deficient, unused or fault data (including drop out and withdrawal) and method for treating unreasonable data

The primary and secondary endpoints will be reported based on the AT Population. Descriptive and summary statistical analysis will be performed on all endpoints. Patient listings for adverse events, deaths, and reinterventions will include all enrolled patients.

All clinically relevant baseline and follow-up variables will be tabulated. Descriptive statistics for continuous variables include mean, standard deviation, sample size, median, minimum, and maximum) and frequency tables or proportions for discrete variables.

Kaplan Meier estimates will be performed at the pre-specified follow-up times to project the estimates for time-related endpoints such as the 30-day mortality rate, the primary endpoint; the standard error and confidence limits will be computed using Greenwood's algorithm. Based on 50 patients as point estimate and length of estimate on the primary endpoint, the 30 days death rate and 95% confidence interval will be summarized.

Echocardiographic data will be analyzed by an Echo core laboratory with respect to the degree of total aortic valve regurgitation (TVR) and paravalvular aortic valve regurgitation (PAR) according to the VARC-2 definitions [29].

These data and other categorical data (e.g., NYHA class) will also be presented as shift from baseline for each of the pre-specified follow-up periods.

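### NYHA class has no dated baseline: the only pre-procedure value is an untimed screening one, so change before implantation can enter the descriptive NYHA shift tables

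*Combined protocol and SAP*

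**What the plan says.** **Where NYHA is collected.** The screening list is introduced by "The following screening data will be collected for all study patients to assess eligibility as per standard of care" and includes "NYHA functional classification". Table 2 (section 7.1.5.2) marks NYHA at Screening, Discharge, 30 days, 1 year and 2-5 years. The Baseline column is empty for it.

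**Which time limits exist.**
- Screening echocardiogram: "Non-Invasive Studies (must be completed within 60 days before procedure date".
- Screening CT and left heart catheterization: up to 180 days before the procedure.
- Baseline visit: "Assessments and laboratory tests are required to be completed within 30 days prior to the procedure date", with anything older repeated. The list covers medications, NIHSS, mRS, frailty, six-minute walk, KCCQ, laboratory tests, ECG and chest x-ray. NYHA and CSS angina class are not on it.
- Inclusion criterion 2: 60 days, for valve area, indexed area, gradient and jet velocity.
- Inclusion criterion 3: "NYHA Functional Class II or greater", with no time limit.

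**Bridging valvuloplasty.** Exclusion 8 rules out BAV in the 30 days before the procedure "unless BAV is a bridge to procedure after a qualifying echocardiogram".

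**How NYHA is used.** The Efficacy list in sections 3.2 and 7.1.6 names NYHA class at 30 days. Section 8.4 adds that "other categorical data (e.g., NYHA class) will also be presented as shift from baseline" for each follow-up period. It does not say which measurement is the NYHA baseline.

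**The concern.** A shift table attributes to the intervention everything that happens between its two readings. For NYHA the first reading has no latest permissible age, and the screening wording lets it come from routine care. Two things can happen between that reading and the implant.

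- The patient changes while waiting. Worsening from class II to III makes the later gain look smaller than it was. Stabilisation after being screened in a poor state makes it look larger.
- The patient has a permitted bridging BAV. Any symptomatic benefit still present is then shown as change after SAPIEN 3.

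The trial is single-arm, so there is no comparison group in which the same drift would appear. The data are intended for a regulatory submission, and shift in functional class is a display that readers tend to take as evidence of benefit.

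**Working it through.** The point concerns timing, so the check sets the schedule, the windows and the analysis text side by side. The arithmetic is short.

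**Step 1. Does any window reach NYHA?** In the Screening section the 60-day limit heads the non-invasive studies, meaning the echocardiogram; NYHA is a separate, earlier bullet. The 180-day limits are attached to CT and catheterization. The 60-day limit in inclusion criterion 2 qualifies the valve measurements. The 30-day limit and repeat rule govern the Baseline list, which omits NYHA. None applies.

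**Step 2. Longest gap from the pre-procedure value to the 30-day visit.** The 30-day visit may take place up to day 30 + 14 = 44. The longest gap is the pre-procedure window plus 44 days.

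| Measurement | Window before procedure | Longest gap |
|---|---|---|
| KCCQ, six-minute walk | 30 days | 30 + 44 = 74 days |
| Echocardiogram | 60 days | 60 + 44 = 104 days |
| CT, catheterization | 180 days | 180 + 44 = 224 days |
| NYHA as written | none stated | no upper bound |
| NYHA placed under the Baseline rule | 30 days | 30 + 44 = 74 days |

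The six-minute walk is not a listed endpoint, yet it has a dated and repeatable baseline. NYHA is a listed endpoint and has neither.

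**Step 3. Can something happen in the gap without a new NYHA reading?** Yes.
- A bridging BAV under exclusion 8 comes after the qualifying echocardiogram by definition and may come after the screening NYHA. No repeat is required.
- A BAV more than 30 days before the procedure is not excluded, and it too may follow the screening NYHA.
- Table 3 provides for the procedure to be put off for 30 days of anticoagulation when thrombus is found. A KCCQ taken before the day it was aborted would then be more than 30 days old and need repeating. NYHA would not.

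**Step 4. Would moving NYHA to the Baseline visit remove the BAV problem?** Only in part. A BAV more than 30 days before the procedure would precede any Baseline visit held within 30 days. A bridging BAV inside the 30 days might not: a Baseline visit on day -25 and a BAV on day -10 satisfy both rules, and the new NYHA value still comes first. KCCQ has the same exposure now. For a bridged patient the qualifying echocardiogram precedes the BAV in every case.

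**Step 5. What one patient is worth.** With 50 to 60 patients in the table, each patient whose pre-implant change alters whether they count as improved moves that proportion by 1/60 = 1.7 to 1/50 = 2.0 percentage points. The documents do not say how many such patients to expect.

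**The case against.** **The shift is not the endpoint.** The Efficacy list names class at 30 days, which needs no pre-procedure value. Section 8.4 presents the shift in addition, with no test, margin or success rule. This stands and limits the point to a descriptive display. A reader might infer that the NYHA endpoint itself, or the trial's conclusion, is compromised; the text does not support that.

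**A very old value is unlikely in practice.** The valve measurements must fall within 60 days, and the heart team and then the sponsor review each case. This makes a long gap less likely, but neither provision dates the NYHA reading or requires it to be repeated.

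**Other functional measures are better timed.** KCCQ and the six-minute walk have baselines within 30 days and are repeated at 30 days, so the trial does have dated functional data. This stands. It does not repair the NYHA table.

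**A reference before BAV is defensible.** The protocol deliberately qualifies bridged patients on the earlier echocardiogram, and the background section says BAV did not give lasting haemodynamic improvement. Change from the qualifying disease state is a legitimate quantity. This is a reason to show results with and without bridged patients instead of removing them from the main table.

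**A fuller SAP may define baseline.** Section 8.5 refers to one. It could say which value to use, but could not supply a later NYHA value that the schedule never collects.

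**The size cannot be derived.** A reader might take the background statement that "the systolic pressure gradient across the valve can increase by as much as 15-19 mmHg per year" and scale it to 180 days: 15 to 19 x 180/365 = 7.4 to 9.4 mmHg. That window belongs to CT and catheterization, the rate is a stated ceiling, and nothing in the documents converts a gradient change into a change of NYHA class.

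**Conclusion.** The point holds as a gap in data collection. If the plan is followed exactly, the NYHA baseline is an untimed screening value, and change before implantation can enter the shift tables at every follow-up period where NYHA is recorded. The direction is not fixed: worsening while waiting understates the gain, and improvement after a bridging BAV overstates it.

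The consequence is confined to the descriptive shift display. NYHA class at 30 days, 30-day mortality and the sample size of 50-60, which was set by regulatory agreement, do not depend on it.

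No size of effect can be given. The documents state neither how often bridging BAV occurs nor how often NYHA class changes before the procedure, and either could be zero. On purely assumed inputs (5-20% of patients bridged, 25-75% of those improved by a class before implantation), the products run from 0.05 x 0.25 = 1.25 to 0.20 x 0.75 = 15 percentage points. That width shows how far the answer depends on the assumption; it is not an estimate.

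A reader might also infer that a dated baseline would isolate the effect of the valve. It would not, because an uncontrolled before-after comparison remains. The change removes an avoidable part of the mixing. It is a cheap improvement worth making, and a missed pre-procedure value cannot be obtained after implantation.

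**What to change.** 1. In Table 2 and the Baseline section, add NYHA class and CSS angina class to the Baseline visit under the existing 30-day and repeat rule. Keep the screening value for eligibility only.
2. In section 8.4, define the baseline for the NYHA shift tables as the last value before the procedure.
3. Flag each patient with a bridging BAV, and record whether their baseline NYHA, KCCQ and echocardiogram came before or after it. This is needed because a Baseline visit within 30 days can still precede the BAV.
4. Keep all patients in the main tables, and repeat the NYHA, KCCQ, gradient and regurgitation change tables without the bridged patients as a sensitivity display.

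The cost is one clinician-assigned classification (with the matching angina class) at a visit that already takes place, one or two CRF fields and one additional set of descriptive output. The sample size does not change. The proportion improved may come out slightly less favourable.
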